Safety data from these two studies (N = 575) showed that the types and frequencies of AEs during upadacitinib treatment were consistent with subjects with moderately to severely active RA receiving immunomodulatory therapy. The incidences of AEs were numerically higher in the upadacitinib dose groups, with a trend toward higher rates with higher doses of upadacitinib. The most frequently reported AEs ( $\geq 5\%$ ) in the upadacitinib treated subjects were urinary tract infection, headache, upper respiratory tract infection, and nausea. There were 6 subjects (1.3% of total combined populations) with herpes zoster reactivation distributed across the upadacitinib dose groups, and 2 subjects (1.9%) in the placebo groups. In these two 12 week studies, a total of 2 subjects in the upadacitinib treatment groups reported malignancies. One subject reported non-melanoma skin cancers (NMSC) (basal cell and squamous cell carcinoma) and 1 subject was diagnosed with lung cancer after the final scheduled visit, and subsequently died 14 weeks after study completion. These events were reported by the Investigators as not possibly related to study drug. Elevations of liver function tests were sporadic with no clear dose-response relationship observed. As observed with other JAK inhibitors, treatment with upadacitinib resulted in an increase in lipids (low-density lipoprotein cholesterol [LDL-C] and high-density lipoprotein cholesterol [HDL-C]). Among subjects with laboratory evidence of systemic inflammation (as evidenced by high-sensitivity C-reactive protein [hsCRP] > upper limit of normal [ULN]), treatment with lower doses of upadacitinib (3 mg BID and 6 mg BID) was associated with improvements in mean hemoglobin relative to placebo. At higher doses, there was a reduction in mean hemoglobin; however, the mean hemoglobin levels remained within normal range throughout the treatment period.

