#### **4.2 Overall Study Design and Plan**

This is a Phase 3, multicenter study that includes two periods. Period 1 is the 24-week randomized, double-blind, parallel-group, placebo-controlled period designed to compare the safety and efficacy of Upadacitinib 30 mg QD and 15 mg QD versus placebo for the treatment of signs and symptoms of subjects with moderately to severely active RA who have an inadequate response to or intolerance to bDMARD therapy and are currently on a stable dose of csDMARDs. Period 2 is a blinded long-term extension to evaluate the

long-term safety, tolerability, and efficacy of Upadacitinib 30 mg QD and 15 mg QD in subjects with RA who have completed Period 1. Starting with Amendment 4, all subjects will receive open-label upadacitinib 15 mg QD, including those currently on upadacitinib 30 mg QD.

The study is designed to enroll approximately 450 subjects at approximately 350 study centers worldwide to meet scientific and regulatory objectives without enrolling an undue number of subjects in alignment with ethical considerations. Therefore, if the target number of subjects has been enrolled, there is a possibility that additional subjects in screening may not be enrolled.

The study duration includes a 35-day screening period; a 24-week randomized, double-blind, parallel-group, placebo controlled treatment period (Period 1); a 236-week blinded extension period (Period 2); and a 30-day follow-up (call or site visit).

Subjects who meet eligibility criteria will be randomized in a 2:2:1:1 ratio to one of four treatment groups:

- Group 1: Upadacitinib 30 mg QD, N = 150 (Day 1 to Week 12) → Upadacitinib 30 mg QD (Week 12 and thereafter)
- Group 2: Upadacitinib 15 mg QD, N = 150 (Day 1 to Week 12) → Upadacitinib 15 mg QD (Week 12 and thereafter)
- Group 3: Placebo, N = 75 (Day 1 to Week 12) → Upadacitinib 30 mg QD (Week 12 and thereafter)
- Group 4: Placebo, N = 75 (Day 1 to Week 12) → Upadacitinib 15 mg QD (Week 12 and thereafter)

Randomization is stratified by number of prior bDMARD (stratum 1: failed 1 or 2 biologics with the same mechanism of action; stratum 2: failed  $\geq 3$  biologics with the same mechanism of action and/or multiple mechanisms of action) and geographic region.

Subjects must have been receiving csDMARD therapy  $\geq 3$  months and have been on a stable dose of csDMARD(s) for  $\geq 4$  weeks prior to the first dose of study drug and must

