#### **Period 1 (24-Week Randomized, Double-Blind Treatment Period)**

Period 1 will begin at the Baseline Visit (Day 1) and will end at the Week 24 Visit. At the Baseline Visit, subjects who meet all the inclusion criteria and none of the exclusion criteria described in the protocol will be enrolled into the study and randomized to double-blind treatment. During this period of the study, subjects will visit the study site at Weeks 1, 2, 4, 8, 12, 16, 20, and 24. A  $\pm 3$  day window is permitted around scheduled study visits. The last dose of study drug in Period 1 is taken the day prior to the Week 24 visit. Subjects who complete Period 1, but decide not to continue in Period 2 should complete a 30 day follow-up visit after the last dose of study drug.

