#### **Period 2 (Blinded Long-Term Extension Period [236 Weeks])**

Period 2 will begin at the Week 24 Visit after all assessments have been completed. During Period 2, subjects will have a study visit at Weeks 36, 48, and every 12 weeks through Week 240, and Week 260/PD. A  $\pm 7$  day window is permitted around scheduled study visits.

Starting at Week 24, at least 20% improvement in BOTH TJC AND SJC is required to remain on study drug. Anyone who does not fulfill this criterion at 2 consecutive visits (starting at Week 24) despite optimization of background RA therapy must be discontinued from study drug.

Starting with Amendment 4, all subjects will receive open-label upadacitinib 15 mg QD, including those currently on upadacitinib 30 mg QD.

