### 10.2.2 Analysis of Long-Term Adverse Event Rates

Long-term adverse event rates will be analyzed using event rates adjusted by cumulative exposure and will be based on the actual treatment received at the time of AE occurrence. Starting with Amendment 4, all subjects will receive open-label upadacitinib 15 mg QD, including those currently on upadacitinib 30 mg QD. For subjects who previously received upadacitinib 30 mg QD, adverse events and exposure to upadacitinib 30 mg QD will be censored at the time of dose switch; subsequent adverse events and exposure

starting the day of first dose of upadacitinib 15 mg QD will be summarized under a separate group. The detailed treatment groups, including the handling of dose switch, are described in Section 8.1.

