#### **10.2.2.1 Overview of Adverse Events Rates per 100 Patient-Years of Study Drug Exposure**

An overview of AEs per 100 patient-years of study exposure will be presented by treatment group and overall for the following AE categories.

- All TEAEs
- Treatment-emergent serious adverse events (SAEs)
- Treatment-emergent severe adverse events
- TEAEs reasonably possibly related to study drug
- TEAEs of special interest
- TEAEs leading to discontinuation of study drug
- TEAE leading to death

For this calculation, 1 year will be considered to be 365.25 days. For each treatment group, the numerator of the overall rate will be the total number of TEAEs reported for the event; that is, a subject can contribute more than one event to the numerator. For each treatment group, the denominator of the rates will be the total number of days exposed to study drug summed across all treated subjects divided by 365.25. Please refer to Section 6.0 for the calculation of study drug exposure. The AE rate per 100 patient-years of exposure will be calculated as  $([\text{numerator}/\text{denominator}]) * 100$ . The number of AEs reported (numerator), the total number of years of study drug exposure (denominator), and the AE rate per 100 patient-years will be presented for each treatment group and overall.

In the AE overview summary, any event with an unknown severity will be considered as severe and any AE with an unknown relationship will be considered as having "reasonable possibility" of being related to study drug.

Additional AEs may be considered for tabulation/summary based on recommendations from Clinical and Safety as deemed appropriate.

For TEAEs of special interest, the point estimate and 95% CI (using normal approximation) will be provided for the treatment difference in AE rate per 100 patient-years between each Upadacitinib dose group and the combined placebo group.

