### **10.2.2.3 Adverse Events of Special Interest Rates per 100 Patient-Years of Study Drug Exposure**

The Adverse Events of Special Interest (AESI) categories will be summarized and presented for each treatment group and overall using SOC and MedDRA PT. The AESI categories will be identified as defined in [Table 8](#). Adjudicated cardiovascular events will be summarized and presented by treatment group using the CAC adjudicated categories.

For each treatment group, the Adverse Events of Special Interest (AESI) rate per 100 patient-years of exposure will be calculated overall, for each SOC and each PT, for each of the AESI listed in [Section 10.2.1.6](#). For this calculation, 1 year will be considered to be 365.25 days. For each treatment group, the numerator of the overall rate, the SOC rate, or the PT rate, will be the total number of TEAEs reported overall, for the SOC, or for the PT, respectively; that is a subject can be counted more than once overall, for a SOC, and for a PT.

For each treatment group, the denominator of the rates will be the total number of days exposed to study drug summed across all treated subjects divided by 365.25. Please refer to [Section 6.0](#) for the calculation of study drug exposure. The AE rate per 100 patient-years of exposure will be calculated as  $[(\text{numerator}/\text{denominator})] * 100$ . The number of AEs reported (numerator), the total number of years of study drug exposure (denominator), and the AE rate per 100 patient-years will be presented overall, for each SOC, and for each PT for each treatment group.

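### SAP 10.2.2.1 compares long-term AESI rates with a placebo group that ends at Week 12, using a normal-approximation interval that is unreliable at that placebo exposure

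*SAP*

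**What the plan says.** SAP 10.2.2 assigns long-term events and exposure to the treatment being taken when the event occurs, using the four exposure groups of Section 8.1: placebo, 15 mg, 30 mg, and 15 mg after a switch from 30 mg. For subjects on 30 mg, "adverse events and exposure to upadacitinib 30 mg QD will be censored at the time of dose switch".

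SAP 10.2.2.1 describes the display: "An overview of AEs per 100 patient-years of study exposure will be presented by treatment group and overall for the following AE categories". AESI are one of its seven categories. A subject may contribute several events to a numerator. For the AESI category, "the point estimate and 95% CI (using normal approximation) will be provided for the treatment difference in AE rate per 100 patient-years between" each dose group and combined placebo. The section gives no variance formula, no rule for sparse counts and no restriction to the first 12 weeks. It does not say whether the post-switch 15 mg group is compared.

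Individual AESI are handled in SAP 10.2.2.3, where the rate "will be calculated overall, for each SOC and each PT, for each of the AESI listed in" Section 10.2.1.6. No difference or interval is mentioned there.

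Placebo is given to 75 + 75 subjects up to Week 12 (SAP 4.2). SAP 10.2.1.1 already provides an AESI percentage difference against placebo over that period. SAP 11.1 states that version 3.0 governs only the long-term reporting still to come.

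**The concern.** Two things are wrong, and they are separate.

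First, the windows do not match. Placebo time is wholly blinded, on stable background csDMARDs, and confined to the first 12 weeks. Upadacitinib time continues past Week 24, when background therapy and corticosteroids may be started or increased. The long-term group is also selected by response: "Anyone who does not fulfill this criterion at 2 consecutive visits (starting at Week 24) despite optimization of background RA therapy must be discontinued". For 15 mg, follow-up includes open-label treatment after Amendment 4 and the COVID-19 period. A difference in rates per 100 PY then mixes treatment with calendar time, time on study and selection. No choice of interval cures this.

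Second, with about 34.5 PY on placebo, a normal approximation has the wrong error rate, and its direction depends on a variance that the SAP does not name.

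Long-term safety is the Period 2 objective, and this is the only placebo contrast in the long-term adverse event section. A reader will take an interval that excludes zero as a safety signal or as reassurance.

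**Working it through.** The documents state neither placebo patient-years nor a precision for this difference, so there is no plan figure to reproduce.

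**Exposure.** SAP 4.2 gives 150 placebo subjects, a 12-week (84-day) course and a ±3-day visit window. SAP 10.2.2.1 sets a year at 365.25 days.
- On schedule: 150 × 84 / 365.25 = 34.5 PY.
- Window limits: 150 × 81 / 365.25 = 33.3 PY and 150 × 87 / 365.25 = 35.7 PY.
- With the 10% dropout of SAP 4.3 and no time credited to dropouts: 135 × 84 / 365.25 = 31.0 PY.
- 15 mg ceiling with no dropout: (150 × 260 × 7 + 75 × 248 × 7) / 365.25 = 1,104 PY. Assumed discontinuation of 10–30% a year gives about 862 to 521 PY.

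At equal rates, placebo supplies T1/(T0 + T1) = 1,104 / 1,138.5 = 97% of the variance. Longer upadacitinib follow-up therefore adds almost no precision.

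**Intervals.** Let x and y be the placebo and upadacitinib event counts over T0 and T1. The difference is d = y/T1 − x/T0, with limits d ± 1.96 × SE.
- Unpooled: SE = √(y/T1² + x/T0²).
- Pooled: SE = √(r(1/T1 + 1/T0)), where r = (x + y)/(T0 + T1).

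**Zero placebo events.** The unpooled lower limit is (y − 1.96√y)/T1. It exceeds zero once y > 3.84, that is from 4 upadacitinib events, at any exposure. Yet the exact upper limit for the placebo rate is 3.689/34.5 = 10.7 per 100 PY. An exact conditional comparison needs (T1/(T0 + T1))^y ≤ 0.025. This gives y ≥ 3.689/ln(334.5/300) = 33.9, so 34 events at 300 PY, and y ≥ 3.689/ln(634.5/600), so 66 events at 600 PY.

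**Error rates.** I enumerated two independent Poisson counts with equal true rates, T0 = 34.5 PY and T1 = 300 to 1,000 PY. The nominal error is 2.5% per tail. The rates are assumptions.

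| Rate per 100 PY | Expected placebo events | Unpooled, false upadacitinib excess |
|---|---|---|
| 60–80 | 20.7–27.6 | 4–5% |
| 40 | 13.8 | 5.0–5.5% |
| 20 | 6.9 | 6.6–7.7% |
| 10 | 3.5 | 10–13% |
| 5.6 | 1.9 | about 15% |
| 1.9 | 0.7 | 43–52% |
| 1 | 0.3 | 25–70% |

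With the pooled variance, the false excess is at most 1.8% at rates up to 40, but the false deficit is 3.1–3.4% at 20–40 per 100 PY and about 4–5% at 1.9 to 5.6.

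The 5.6 is the one rate with an anchor in the documents. Protocol 3.0 reports: "There were 6 subjects (1.3% of total combined populations) with herpes zoster reactivation distributed across the upadacitinib dose groups", and 2 subjects (1.9%) on placebo, among 575. These figures fit about 469 and 106 subjects. At 84 days each, upadacitinib exposure is 469 × 84 / 365.25 = 107.9 PY, and 6/107.9 = 5.6 per 100 PY. Six subjects give an exact 95% interval of 2.0 to 12.1, so it is only a rough guide.

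**Repeat events.** A subject can be counted more than once, so counts may vary more than Poisson counts do. At 600 v 34.5 PY and 20–40 per 100 PY, I assumed a variance-to-mean ratio of 1.5 and then 2. An interval combined from exact Poisson limits, whose tails are at most about 2% without clustering, then has tails of 3.1–4.7% and 5.2–7.2% respectively. The unpooled false excess rises to 9–16% over the two ratios.

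**The case against.** The strongest reply is that the interval belongs to the single aggregate AESI row. The wording supports this: AESI are one category in the overview, and 10.2.2.3 gives each AESI a rate but no difference. Table 8 of the SAP pools many categories, including anemia, CPK elevation, hepatic disorder and serious infection, so the aggregate rate may be high. At 60–80 per 100 PY the false excess is only 4–5%. This stands, and it sets the size of the problem. It leaves the mismatch of windows untouched.

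It is also fair that the display carries no p-value or decision rule, that counts and patient-years appear beside the rates, and that a duration-matched placebo comparison exists in 10.2.1.1. These limit the harm to misreading. They also make the long-term contrast easy to give up.

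A third reply is that exact Poisson limits are no remedy while repeat events are counted. That is right, and it changes the fix.

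A reader might infer from the lower rows of the table that the long-term report will usually show false signals for rare events. The documents do not support that. It would require an interval for each AESI, which the SAP neither specifies nor rules out. Nor does the error necessarily run against upadacitinib: a pooled variance errs toward a false deficit.

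**Conclusion.** The concern holds as a should-fix on a descriptive display. The comparison of unmatched windows is a defect under any interval, because constant rates over time are neither stated nor justified. The normal approximation adds to it. On the likelier, aggregate reading, the false excess is two to three times nominal at 20–40 per 100 PY with an unpooled variance, and the false deficit is modestly above nominal with a pooled one. The double-digit errors at 10 per 100 PY and below matter chiefly if single AESI are also compared.

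These sizes rest on assumed event rates, upadacitinib exposure of 300 to 1,000 PY, equal true rates and independent Poisson counts. Clustering of repeat events would make them worse. Placebo dropout would lower exposure from 34.5 PY toward 31 PY. Nothing here touches the Week 12 safety comparison or the efficacy results.

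**What to change.** In SAP 10.2.2.1, delete the long-term AESI rate difference against placebo and point to the Week 12 contrast in 10.2.1.1, which needs no change. Report long-term AESI rates for each Section 8.1 exposure group with an interval that suits the count: exact Poisson limits for subjects with a first event per person-time at risk, or a subject-level robust or bootstrap interval for event-count rates.

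If the difference is kept:
- base it on first-event subject counts, with an interval combined from the two sets of exact limits, or give an exact conditional rate ratio;
- state whether it covers the aggregate row, each AESI, or both;
- state whether the group switched from 30 mg to 15 mg is compared with placebo;
- footnote that the two rates come from different time windows.

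The cost is SAP wording and minor programming, with no new data. The long-term placebo contrast is lost or its interval widens, and first-event rates answer a slightly different question from event-count rates. The loss is small. Comparison with placebo is the Period 1 objective, and Protocol 8.1.5.2.1 asks only for AESI event rates in the combined analysis.

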#### **10.2.2.2 Adverse Events Rates per 100 Patient-Years of Study Drug Exposure by SOC and PT**

For each treatment group, the TEAE rate per 100 patient-years of exposure will be calculated overall, for each SOC and each PT, for each of the following events:

- All TEAEs
- Treatment-emergent serious adverse events (SAEs)
- Treatment-emergent severe adverse events
- TEAEs reasonably possibly related to study drug
- TEAEs leading to discontinuation of study drug
- TEAE leading to death

For this calculation, 1 year will be considered to be 365.25 days. For each treatment group, the numerator of the overall rate, the SOC rate, or the PT rate, will be the total number of TEAEs reported overall, for the SOC, or for the PT, respectively; that is a subject can be counted more than once overall, for a SOC, and for a PT. For each treatment group, the denominator of the rates will be the total number of days exposed to study drug summed across all treated subjects divided by 365.25. Please refer to Section 6.0 for the calculation of study drug exposure. The AE rate per 100 patient-years of exposure will be calculated as  $[(\text{numerator}/\text{denominator})]*100$ . The number of AEs reported (numerator), the total number of years of study drug exposure (denominator), and the AE rate per 100 patient-years will be presented overall, for each SOC, and for each PT for each treatment group.

### **10.2.2.3 Adverse Events of Special Interest Rates per 100 Patient-Years of Study Drug Exposure**

The Adverse Events of Special Interest (AESI) categories will be summarized and presented for each treatment group and overall using SOC and MedDRA PT. The AESI categories will be identified as defined in [Table 8](#). Adjudicated cardiovascular events will be summarized and presented by treatment group using the CAC adjudicated categories.

For each treatment group, the Adverse Events of Special Interest (AESI) rate per 100 patient-years of exposure will be calculated overall, for each SOC and each PT, for each of the AESI listed in [Section 10.2.1.6](#). For this calculation, 1 year will be considered to be 365.25 days. For each treatment group, the numerator of the overall rate, the SOC rate, or the PT rate, will be the total number of TEAEs reported overall, for the SOC, or for the PT, respectively; that is a subject can be counted more than once overall, for a SOC, and for a PT.

For each treatment group, the denominator of the rates will be the total number of days exposed to study drug summed across all treated subjects divided by 365.25. Please refer to [Section 6.0](#) for the calculation of study drug exposure. The AE rate per 100 patient-years of exposure will be calculated as  $[(\text{numerator}/\text{denominator})] * 100$ . The number of AEs reported (numerator), the total number of years of study drug exposure (denominator), and the AE rate per 100 patient-years will be presented overall, for each SOC, and for each PT for each treatment group.

### **10.2.2.4 Listing of Serious Adverse Events (Including Deaths) and Adverse Events Leading to Study Drug Discontinuation**

All serious adverse events (SAEs), deaths, and adverse events leading to discontinuation of study drug will be listed.

### **10.3 Analysis of Laboratory Data**

#### **10.3.1 Variables and Units**

All laboratory parameters to be collected in this study are listed below. Laboratory parameters will be reported using the standard international (SI) units.

**Table 9. List of Laboratory Variables**

---

Laboratory Variables
Hematology
White Blood Cell (WBC) Count
Red Blood Cell (RBC) Count
Hemoglobin
Hematocrit
Platelets count
Neutrophils
Basophils
Eosinophils
Lymphocytes
Monocytes
Bands
Chemistry
Total Bilirubin
Alkaline Phosphatase (ALP)
Aspartate aminotransferase (AST)
Alanine aminotransferase (ALT)
Total Protein
Albumin
Glucose
Triglycerides
Blood Urea Nitrogen (BUN)
Creatinine
Uric acid
Sodium

---

**Table 9. List of Laboratory Variables**

---

Laboratory Variables
Chemistry (Continued)
Potassium
Calcium
Inorganic Phosphorus
Creatine Phosphokinase (CPK)
Chloride
Bicarbonate
Cholesterol
LDL cholesterol
HDL cholesterol
LDL/HDL ratio
Cholesterol/HDL ratio
Urinalysis
Specific Gravity
pH
Protein
Glucose
Ketones
Blood
Microscopic Examination (if needed)
Urobilinogen
Bilirubin
Leukocytes
Nitrites
Other
hs-CRP
QuantiFERON-TB Gold a
IgG and IgM
ESR
TBNK
Additional TBNK

---

a. For annual follow-up QFT is captured only for those with negative QFT at Screening.

